11.2 Karolinska Sleepiness Scale

The KSS [3] will be used to assess subjective level of sleepiness. This is a subject self-report measure of situational sleepiness and provides an assessment of alertness/sleepiness at a particular point in time. The KSS has been found to correlate with electroencephalogram and behavioral variables [4]. Subjects indicate their level of alertness versus sleepiness according to the following scale:

Karolinska Sleepiness Scale

- 1=extremely alert
- 2
- 3=alert
- 4
- 5=neither alert nor sleepy
- 6
- 7=sleepy - but no difficulty remaining awake
- 8

9=extremely sleepy – fighting sleep

Subjects will self-report their KSS assessments at the times specified in [Section 10](#). The subject's self-reported scores will be recorded in the case report form (CRF).

11.3 Self-perceived Safety to Drive Question

Prior to driving, the subject will be asked a simple question as to whether they feel safe to drive (“Right now do you feel safe to drive?”). The subject will answer “yes” or “no”. The answer will be recorded in the CRF.

11.4 Digit Symbol Substitution Test (CogScreen Symbol Digit Coding; SDC)

The CogScreen SDC subtest will be used in this study to measure attention, visual scanning, working memory, and speed of information processing. SDC is a computer analogue of the conventional symbol-substitution task found in the WAIS-R Digit Symbol subtest and the Symbol Digit Modalities Test [5].

SDC will be administered by trained study site personnel. Subjects will perform the test prior to the driving simulation test at the times specified in [Section 10](#). The subject will perform the test by interacting with a touchscreen monitor. Data will be captured in electronic format. Details are provided in the CogScreen® Examiner Manual, CogScreen LLC, 2016.

11.5 Visual Analog Scales (VAS) to Assess Subject's Motivation and Self-Appraisal

After completing the driving simulation, subjects will assess their own performance and their level of motivation to perform at their best during the driving simulation.

Subjects will respond to 2 questions:

1. How well you think you drove for the last 60 minutes?
2. How motivated did you feel to drive at your best during the last 60 minutes of driving?

Subjects will record their response to each question by drawing a vertical line on a 100 mm horizontal, linear visual analog scale. For the self-assessment of driving performance, one end of the line is marked “Not Satisfactory” and the other end of the line is marked “Satisfactory”. For the motivation item, one end of the line is marked “Not Motivated” and the other end is marked “Motivated”. Scores on the 100 mm linear scale will be measured to the nearest millimeter from the left. The subject's scores will be recorded in the CRF.

11.6 Vital Signs

Vital signs will include the measurement of supine and standing blood pressure and heart rate, respiration rate, and body temperature. Weight and height will be measured at Screening only.

11.7 Clinical Laboratory Assessments

A certified laboratory will be used to perform all routine hematology, clinical chemistry, and urinalysis. Planned laboratory analyses include:

Category	Test Name
Hematology	Hemoglobin Hematocrit Platelets Prothrombin Time (PT) ^c Red blood cells White blood cells with differential (absolute)
Chemistry	Alanine aminotransferase (ALT) Aspartate aminotransferase (AST) Alkaline phosphatase Blood urea nitrogen (BUN) Creatinine Gamma glutamyltransferase (GGT) Glucose Potassium Sodium Total and direct bilirubin Thyroid stimulating hormone (TSH) ^c
Urinalysis	Bilirubin Erythrocytes Glucose Ketones Leukocytes Nitrite pH Protein Specific gravity Urobilinogen
Other	Urine drug and alcohol breathalyzer ^{a,b} Serum/urine Pregnancy ^d

^a Screening and end of study (EOS) (Day 17). ^b Includes testing for amphetamines, methamphetamines, barbiturates, benzodiazepines, cannabinoids, cocaine, ethanol and opiates – ethanol will be determined by breathalyzer. ^c Screening only. ^d Serum pregnancy at Screening and urine pregnancy test at check-in for each period (Days -1, 7, and 14) for females of childbearing potential. Note: The complete panel of safety labs (other than where footnoted) will be completed at Screening and EOS (Day 17).
	

11.8 Blood Collection for Tolperisone Plasma Concentrations

Blood samples for the determination of plasma tolperisone concentrations will be drawn prior to each AM dosing on Days 1-3 and post-driving test (15-30 minutes after the drive) on Days 1 and 3.

Blood samples will be collected into heparinized polypropylene tubes (~5.0 mL). The tubes should be mixed immediately after filling by gently inverting the tubes at least 8 to 10 times. Thereafter, the tubes will be centrifuged as soon as possible (within 30 minutes of collection) at a minimum of 1500 g for 15 minutes until cells and plasma are well separated. The resulting

plasma samples will be transferred into two (duplicate) 2 ml cryovial tubes and labeled appropriately.

Plasma samples will be analyzed for tolperisone at Pharm-analyt Labor GmB, [name], using a validated liquid chromatography with tandem mass spectrometric detection (LC/MS/MS) method (limit of quantification (LOQ): 1 ng/mL). A detailed method description, including validation, calibration and quality assurance procedures will be included in the bioanalytical report which will be part of the Final Study Report.

11.8.1 Sample Storage and Shipment

The samples will be frozen as soon as possible (within 4 hours) of collection and stored frozen at -20°C until time of shipment to Pharm-Analyt Labor, GmB, [name] for analysis. All samples will be shipped frozen with sufficient dry ice to maintain frozen conditions for at least 72 hours at times arranged between the study site and the analytical laboratory. Detailed shipping instructions will be provided separately.

11.9 Blood Collection Volume for the Study

For Periods 1-3, a total of approximately 25 mL (5 x 5 mL samples) will be collected from each subject for PK analysis. In addition, up to 48 mL of blood will be collected for screening and EOS clinical laboratory evaluations.

11.10 Medical and Social History

A medical and social history will be performed at Screening. Each subject's history of alcohol and drug use will be evaluated. Subject's caffeine consumption and tobacco use will be evaluated to ensure that the protocol will be followed during the course of the study. Continued eligibility will be evaluated on Day -1 and adherence to protocol restrictions will be confirmed throughout the study.

11.11 Physical Examination

A physical examination will be performed at Screening and EOS.

11.12 Epworth Sleepiness Scale

The ESS will be used to exclude subjects who demonstrate excessive sleepiness prior to randomization.

The ESS is an 8-item self-administered questionnaire which measures general level of daytime sleepiness. Individual items on the scale refer to daytime events likely to lead to sleepiness. For each item, the subject rates how likely they are to fall asleep. Subjects are asked to rate how likely they would be to doze off or fall asleep in each situation in contrast to feeling just tired based on their usual way of life in recent times. Each item (or situation such as sitting and reading) is rated on a 4-point scale that ranges from "0 = Would never doze" to "3 = High chance

of dozing.” The total score on the ESS is the sum of the responses to each of the 8 items. The range of possible scores for each responder is 0 to 24. A total score of <10 indicates that the individual is not likely suffering from excessive daytime sleepiness. Individual items are not analyzed and have no independent, valid interpretations.

Subjects will complete the ESS at Screening.

11.13 Pregnancy Test

A serum pregnancy test will be performed at Screening for all females of childbearing potential. A urine pregnancy test will also be collected at each CRU check-in visit (Days -1, 7, and 14) for females of childbearing potential. A positive pregnancy test at any time during the study will immediately terminate the subject from further participation in the study.

11.14 Study Drug Preparation and Dispensing

The Sponsor will supply Tolperisone 150 mg tablets and matching placebo in an unblinded fashion. The sites or CRO on behalf of the sites will procure the cyclobenzaprine 10 mg tablets. To maintain the double-blind status of the study, the following dispensing and dosing procedures will be followed. The site will identify a qualified unblinded dispenser and alternate(s) who will be responsible for dispensing and administering the study treatment. Aside from dispensing and administering the study treatment, the qualified unblinded dispenser will not be otherwise involved in the study. Cognitive Research Corporation will provide randomization codes directly to the individual identified by the study site. The randomization codes will be kept in a secured area with access limited to only the assigned unblinded dispenser.

The qualified unblinded dispenser will prepare study treatment for each subject in a designated dispensing room. Prior to administering the first dose, the qualified unblinded dispenser will assign the next available randomization number. For each dose administered, the unblinded dispenser will dispense the appropriate tablet into a dispensing cup and complete the study treatment dispensing record. The study treatment dispensing record will remain in a secure locked area with access limited to the qualified unblinded dispenser and the alternate(s). No other study personnel will be present in the designated dispensing room at the time of study treatment dispensing.

11.15 Study Drug Administration

To maintain the study blind for tolperisone 150 mg, cyclobenzaprine 10 mg, and placebo, subjects will be blindfolded during dosing in each Period. Subjects will be given one tablet at approximately 8:00 AM, 2:00 PM, and 10:00 PM daily on Days 1, 2, 8, 9, 15, and 16 and at 8:00 AM on Days 3, 10, and 17. Dosing will be observed by a study staff member (qualified unblinded dispenser); no other study personnel will be present at the time of dosing.

The qualified unblinded dispenser will place the tablet into a dispensing cup. The blindfolded subject will transfer the study treatment directly from the cup into their mouth. All study medications will be administered orally with 4-6 ounces of room temperature water. The subjects

will be instructed to swallow the study tablet whole, without chewing the tablet. Mouth and hand checks will be performed by CRU personnel for each dose of study drug administered.

11.16 Concurrent Medication

- Subjects are to abstain from using psychoactive prescription or non-prescription medications, psychoactive nutritional supplements or herbal preparations within 2 weeks or 5 half-lives (whichever is longer) of Day 1.
- Subjects are to abstain from using any other medication or dietary supplement to promote sleep, including over the counter sleep medications, during their participation in the study.
- Subject will abstain from using antihistamine or any other drugs that can cause drowsiness, and will discuss any new prescription with the investigator.
- No other medications (with the exception of birth control) are to be taken by the subjects without prior approval from the Principal Investigator and the Sponsor unless it is a medical emergency. All concomitant medication taken during the trial should be recorded with indication, daily dose, and start and stop dates of administration.

11.17 Fluid, Food, and Lifestyle Restrictions

- Subjects are not allowed to consume alcoholic beverages from 48 hours prior to admission to the CRU on Days -1, 7, and 14 until discharged from the CRU following completion of all procedures of each Period on Days 3, 10, and 17. At all other times, alcohol consumption is limited to no more than 3 alcoholic beverages or equivalent (beer [284 mL], wine [125 mL], or distilled spirits [25 mL]) per day.
- The subject will be cautioned regarding the operation of automobiles or other dangerous machinery, and activities made hazardous by decreased alertness. Subjects should also be cautioned that the CNS effects of tolperisone and or cyclobenzaprine may be additive to those of alcohol and other CNS depressants.
- Subjects are not allowed to consume caffeine containing products from approximately 1 pm on the days of admission to the CRU (Days -1, 7, and 14) until discharged from the CRU following completion of all procedures on Days 3, 10, and 17. At all other times, caffeinated beverages will be permitted to no more than 4 units per day amounts (1 unit = 120 mg caffeine).
- Subjects are to refrain from vigorous physical activity from 24 hours prior to admission to the CRU on Days -1, 7, and 14 until discharged from the CRU following completion of all procedures on Days 3, 10, and 17.

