10.2 Study Periods

10.2.1 CRU Admission Days (Visits 2, 6, and 10: Days -1, 7, and 14)

Within 28 days after the Screening visit, eligible subjects will return for Period 1 (Visit 2). Subjects who meet the inclusion and no exclusion criteria will be instructed to return to the clinic on Day -1 at approximately 4:00 PM. The following will be done on Days -1, 7, and 14:

- A urine pregnancy test will be performed for all females of childbearing potential upon admission to the unit.
- The alcohol breathalyzer and drug screen will be repeated.
- Continued subject eligibility will be verified.
- Dinner will be served at 5:00 PM.

- Subjects will be administered a practice trial of the CogScreen SDC test beginning at approximately 7:40 PM.
- A practice drive (approximately 20 minutes) will be performed on the driving simulator beginning at approximately 8:00 PM.
- Vital signs will be measured.
- Any concurrent medication use will be recorded.
- AEs will be assessed

Subjects will spend the night at the CRU and will go to bed at 10:00 PM.

10.2.2 CRU Inpatient Day 1 (Visits 3, 7, and 11: Days 1, 8, and 15)

On Days 1, 8, and 15, subjects will be awakened and fed a standard breakfast at approximately 6:00 AM. A pre-dose pharmacokinetic (PK) blood sample will be taken within 30 minutes before the first dose. Vital signs will be taken at 7:55 AM (± 5 minutes). Subjects will be randomized to a treatment sequence on Day 1 and will be dosed with study medication (tolperisone 150 mg, cyclobenzaprine 10 mg, or placebo) according to the randomization schedule at 8:00 AM (± 5 minutes) on Days 1, 8, and 15.

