with the CVDA driving scenario on the CRCDS-MiniSim. Upon completion of the driving scenario, subjects will be administered visual analog scales to assess their motivation and self-appraisal of their driving performance. Following completion of the VAS, a pre-dose PK blood sample will be drawn. Vital signs will be taken at 7:55 AM (± 5 minutes). Subjects will then be dosed with study medication (tolperisone, cyclobenzaprine, or placebo) at 8:00 AM (± 5 minutes).

Subjects will be fed a standard lunch at approximately 11:30 AM. Prior to receiving the 2nd dose, vital signs will be taken at 1:55 PM (± 5 minutes). Subjects will then be dosed with study medication (tolperisone, cyclobenzaprine, or placebo) at approximately 2:00 PM. A standard dinner will be provided at approximately 5:00 PM.

Subjects will receive their 3rd dose of study drug at 10:00 PM (± 5 minutes). They will spend the night at the CRU and will go to bed immediately following the 3rd dose. AEs and concurrent medication use will be recorded each day.

10.2.4 Clinic Discharge Days (Visits 5, 9, and 13: Days 3, 10, and 17)

On Days 3, 10, and 17, subjects will be awakened and fed a standard breakfast at approximately 6:00 AM. A pre-dose PK blood sample will be taken within 30 minutes before the first dose. Prior to dosing, vital signs will also be taken at 7:55 AM (± 5 minutes). Subjects will then be dosed with study medication (tolperisone, cyclobenzaprine, or placebo) at 8:00 AM (± 5 minutes).

At approximately 8:40 AM, subjects will be administered the CogScreen SDC Test and KSS, and indicate their self-perceived safety to drive. Subjects will then be tested (approximately 1 hour after the 1st dose) on the CVDA driving scenario on the CRCDS-MiniSim. Upon completion of the driving scenario, subjects will be administered visual analog scales to assess their motivation and self-appraisal of their driving performance. A PK blood sample will be taken between 1.5 and 2 hours after the start of the drive (approximately 10:30 AM to 11:00 AM). Subjects will be fed a standard lunch at approximately 11:30 AM.

Prior to discharge from the CRU, the following will be performed:

- AEs will be recorded.
- Any concurrent medication use will be recorded.
- Vital signs will be measured at 1:55 PM (± 5 minutes).

Subjects will leave the clinical site at approximately 2:00 PM. However, they will be advised to stay at the clinical site, if judged necessary by the physician in charge, for safety reasons.

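### Protocol 11.17 permits alcohol from discharge, 6 h after a dose, although the same section warns of additive CNS effects (minor safety point)

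*Protocol*

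**What the plan says.** Protocol section 11.17 (Fluid, Food, and Lifestyle Restrictions) prohibits alcohol starting 48 h before admission on Days -1, 7 and 14. The ban runs "until discharged from the CRU following completion of all procedures of each Period on Days 3, 10, and 17". It continues: "At all other times, alcohol consumption is limited to no more than 3 alcoholic beverages or equivalent" per day, with serving sizes given as 284 mL beer, 125 mL wine or 25 mL spirits.

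The next bullet holds two cautions. One is on driving and hazardous tasks: "The subject will be cautioned regarding the operation of automobiles or other dangerous machinery, and activities made hazardous by decreased alertness". The other is that subjects be told that "the CNS effects of tolperisone and or cyclobenzaprine may be additive to those of alcohol and other CNS depressants". Neither caution has a stated end.

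On timing, section 11.15 sets dosing at 8:00 AM, 2:00 PM and 10:00 PM, with this calendar: "daily on Days 1, 2, 8, 9, 15, and 16 and at 8:00 AM on Days 3, 10, and 17". For the discharge days, section 10.2.4 says "Subjects will leave the clinical site at approximately 2:00 PM", with the qualification that "they will be advised to stay at the clinical site, if judged necessary by the physician in charge, for safety reasons". Nothing in the protocol or SAP text available for this review extends the alcohol ban past discharge.

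**The concern.** The written rule gives express permission to drink on the afternoon of a dosing day, next to a warning that the study drugs may add to the effect of alcohol. Appendix 1 (cyclobenzaprine prescribing information) repeats the warning for cyclobenzaprine and gives it an effective half-life of 18 h (range 8 to 37 h), so most of the drug present after the last dose is still there 6 h later.

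The subjects are healthy volunteers with no treatment benefit. Section 13.1 expects cyclobenzaprine to worsen SDLP by more than 4.4 cm, the effect this scenario showed at 0.05% blood alcohol. Section 11.16 bars sleep aids for the whole of participation and also bars other drugs that cause drowsiness, with no release at discharge. Alcohol is the one depressant released there.

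Only the unblinded dispenser knows which period is cyclobenzaprine (sections 9.3 and 11.14), so a rule meant for that period has to cover all three.

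What is at stake is participant safety only. All drives of a period are finished before discharge, and the 48 h pre-admission ban protects the next period.

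**Working it through.** **Inputs**
- Doses within a period (section 11.15), in hours from the first dose: 0, 6, 14, 24, 30, 38, 48.
- Day 3 drive about 1 h after the last dose (section 10.2.4): t = 49.
- Discharge at about 2:00 PM (section 10.2.4): t = 54.
- Cyclobenzaprine half-life h = 18 h, range 8 to 37 h (Appendix 1, Pharmacokinetics).
- Check-in at about 4:00 PM. Section 10.2.1 states this time only for Day -1 ("will be instructed to return to the clinic on Day -1 at approximately 4:00 PM"); using it for Days 7 and 14 is an assumption.

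**Check against the label's own figure.** Accumulation on 8-hourly dosing is 1/(1 − 2^(−8/h)). At h = 18 this is 3.77, which agrees with the label's statement of about 4-fold.

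**Interval from last dose to discharge.** 8:00 AM to 2:00 PM is 6 h. The fraction remaining from the level just after that dose is 2^(−6/18) = 0.79 (0.59 at 8 h; 0.89 at 37 h).

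**Exposure.** Take one dose as 1 unit with instantaneous absorption: load(t) = sum over doses given by time t of 2^(−(t − tᵢ)/h). At discharge with h = 18, the seven terms are 0.125 + 0.157 + 0.214 + 0.315 + 0.397 + 0.540 + 0.794 = 2.54.

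| | h = 8 | h = 18 | h = 37 |
|---|---|---|---|
| Day 3 drive (t = 49) | 1.70 | 3.08 | 4.49 |
| Discharge (t = 54) | 1.10 | 2.54 | 4.09 |
| Discharge / drive | 0.65 | 0.82 | 0.91 |
| 24 h after discharge (t = 78) | 0.14 | 1.01 | 2.61 |
| 50 h after discharge (t = 104) | 0.01 | 0.37 | 1.60 |

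**Benchmark against labelled use.** The steady-state trough on 10 mg every 8 h is r/(1 − r) with r = 2^(−8/h): 1.00, 2.77 and 6.18 for h = 8, 18 and 37. Discharge load divided by trough is 1.10, 0.92 and 0.66.

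**Sensitivity to absorption.** The documents give no absorption rate, so first-order rates of 0.4 and 1.0 per h are assumed. At h = 18:
- Discharge load is 2.71 (0.4 per h) or 2.64 (1.0 per h).
- The steady-state minimum is 3.02 or 2.88, so discharge load is 0.90 or 0.92 of it.
- The discharge-to-drive ratio rises to 102% or 94%. Over half-lives of 8 to 37 h and both rates it runs from 83% to 105%.

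The instantaneous-absorption ratio of 82% is therefore on the low side.

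**Length of the permitted window.** Day 3 at 2:00 PM to Day 7 at 4:00 PM is 98 h; less the 48 h ban, 50 h remain. Days 10 to 14 are the same. Check-in between noon and 8:00 PM would give 46 to 54 h. After Day 17 no further ban applies. Over 50 h the load falls to 2^(−50/h) of its discharge value: 15% at 18 h, 1% at 8 h, 39% at 37 h.

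**Number of exposures.** Each completer has one cyclobenzaprine discharge, so about 30 in all.

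**The case against.** The strongest reply is that the plan already recognises and manages this risk. It caps intake at three defined small servings, cautions about alcohol and hazardous activity with no end date, and lets the physician advise a longer stay. It also follows the label: 10 mg three times a day is a labelled dose, the label warns about alcohol and hazardous tasks, and alcohol is not among its contraindications. At the 18 h half-life, discharge exposure is slightly below a labelled steady-state trough. The load figures concern one period in three; the documents give no tolperisone half-life, and placebo carries no such risk. The length of any extension is a judgement and is not derived from a safety threshold. Consent pages are not available, so what subjects are told there is unknown.

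These points stand, and they keep the matter minor. They do not remove it. A caution without a duration, placed beside an express allowance, protects less than a short ban. The longer stay helps subjects who look impaired at 2:00 PM, but does not cover drinks taken that evening. Labelled users have a treatment benefit, and the label recommends 5 mg for most patients, with 10 mg reached on individual response; these volunteers start at 10 mg with no benefit. The model's simplicity does not reverse the reading, because allowing for absorption raises the ratio to the drive.

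**Conclusion.** The concern holds as a minor, optional safety improvement. Section 11.17 permits alcohol 6 h after a dose, when modelled cyclobenzaprine load is 2.54 single-dose units (1.10 to 4.09 over the labelled half-life range), or 82% (65% to 91%) of the load at the Day 3 drive. The permission lasts about 50 h after Days 3 and 10 and is open-ended after Day 17.

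The wording of the rule and the 6 h interval are certain. The load figures rest on a one-compartment superposition model and the label's half-life, and they measure exposure, not demonstrated impairment. The 50 h figure rests on a 4:00 PM check-in. No endpoint, sample size or analysis is affected.

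**What to change.** In section 11.17, extend the alcohol ban for all subjects in every period. After Days 3 and 10, continue it from discharge until the existing 48 h pre-admission ban begins; after Day 17, apply it for about 2 days. Give the driving and hazardous-activity caution the same stated duration. The investigator and Medical Monitor should settle the exact length, since about 2 days still leaves 39% of the discharge load at a 37 h half-life.

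The cost is one or two sentences, with no new visit, test, staff or analysis change. The downside is about 2 more days of self-reported abstinence after each of three discharges, which, joined to the existing bans, makes abstinence continuous from 48 h before Day -1 to about Day 19.
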